Appendix 1 - Schedule of assessments			
Appendix 2 - CE Certificate			
Appendix 3 - St Mark's Incontinence Score			
Appendix 4 - Quality of Life Questionnaire			

Appendix 5 - Protocol for MAPLe	
References	40

List of abbreviations

AE	Adverse Event
CI	Chief Investigator
CRF	Case Report Form
FI	Faecal Incontinence
MAPLe	Multiple Array Probe Leiden
AUS	Anal Ultra Sound
HRAM	High Resolution Anal Manometry
ARP	Anorectal Physiology
EMG	Electromyography
sEMG	Surface Electromyogrphy
GCP	Good Clinical Practice
IB	Investigator's Brochure
ICF	Informed Consent Form
ISF	Investigator Site File
MDT	Multi-Disciplinary Team
NHS R&D	National Health Service Research & Development
PI	Principal Investigator
PIS	Participant Information Sheet
QA	Quality Assurance
QC	Quality Control
REC	Research Ethics Committee
SAE	Serious Adverse Event
SDV	Source Document Verification
SOP	Standard Operating Procedure
TMG	Trial Management Group
TSC	Trial Steering Committee

1. Trial personnel

See protocol cover page for Chief Investigator and Sponsor contact details.

Statistician

[name]

e-mail: [contact]

[contact]

2. Summary

Objectives:	Primary Objective: To determine the role of MAPLe in the assessment of Faecal Incontinence (FI) in defined patient groups. Secondary Objective: Identify which patient groups benefit from physiological testing with MAPLe and receive targeted treatment
Type of trial:	This is a multi-centre cohort study investigating FI
Trial design and methods:	The study will take place across two trusts with specialist pelvic floor services.
	Participants will be recruited via referrals for anorectal physiology (ARP) with symptoms of FI meeting the inclusion/exclusion criteria.
	Participants will complete incontinence and quality of life questionnaires, undergo routine ARP with high resolution manometry (HRAM) and anal ultrasound (AUS), and additional assessment with MAPLe. Each assessment will be performed in accordance with a standardised protocol.
	ARP results will be discussed at the local MDT, should treatment be offered, the participant will undergo further testing with MAPLe, if no treatment if offered participation is complete.
Trial duration per participant:	12 months
Estimated total trial duration:	18 months
Planned trial sites:	Multi-Site: University College London Hospitals (UCLH)
	Ashford and St Peter's NHS Foundation Trust (ASPH)
Total number of participants planned:	120

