Main inclusion/exclusion criteria:	Inclusion: Symptoms of FI, aged over and including 18, capacity to consent, male/female. Exclusion: anal cancer, anal surgery in the last 3 months, acute/painful perianal disease.
Statistical methodology and analysis:	Non-inferiority testing of MAPLe in the assessment of FI will be performed using Bland Altman method. MAPLe will be tested against HRAM and AUS.
	Participants will be grouped according their pathology: Fistula/chronic perianal disease, Obstetric injury <12 months, Obstetric injury >12 months, neuropathic sphincter. Correlation studies and regression analysis to identify which groups benefitted from MAPLe assessment.
	The clinical utilisation of MAPLe will be determined by the outcome of an expert panel.
	Comparative analysis of participant pre and post treatment MAPLe results will identify if targeted treatment has been achieved.

3. Background and Rationale

Burdon of Disease

Faecal incontinence (FI) is defined as the involuntary passage of gas, liquid or solid stool. The symptom is experienced by an estimated 1-10% of the population. FI is associated with a multitude of disease pathologies and prevalent in vulnerable patient groups, the elderly, learning disabilities or severe co-morbidities, and most prevalent in multiparous females. The degree of symptomatic severity is varied and can result in psychological destress and social withdrawal, severely impacting quality of life in up to 22% of suffers(1).

There is significant economic burden associated with FI. Health economic studies have identified US\$4110 as an average annual cost per person, with an increased cost associated with increased symptom severity(2). Further studies estimated a US \$11 billion annual expenditure and a 55% increase in personal cost of health for sufferers(3). Treatment is symptom orientated, further research would improve understanding of the symptom and direct treatment for more effective outcomes.

Anatomy and Physiology of the Pelvic Floor

FI is the result of impairment to the structure or function of the pelvic floor(4). The pelvic floor, levator ani, is a sheet of muscle supporting the weight of the abdominal cavity. It is divided into four muscle groups: pubococcygeus, ilio-coccygeus, coccyges and puborectalis, assisting the maintenance of faecal and urinary continence.

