Studies performed at other centers have investigated the use of surface electrodes (sEMG) on probes(34) placed anally to identify abnormalities or abnormal variants in the innervation and propagation of stimulus within the EAS(35). The anal probes have a series of circumferential sensors that identify the origin and direction of propagation of an action potential. The origin correlates to the

location of an NMJ and innervation zone(19). This technique has been used to investigate asymmetric innervation of the anal canal, particularly important in obstetric medicine(36), but has not progressed from research into clinical utilisation.

The MAPLe device is a new medically certified device distributed by Novuqare using the principals of sEMG in the diagnosis and management of pelvic floor complaints (figure 1).

Figure 1 MAPLe device: anal probe, sEMG detector and charging station.

The probe l has 24 surface electrodes positioned in circumferential bands along its length (figure 2), it is placed in the anal canal. Each sensor detects the sEMG activity in mV for the most proximal muscle fibers (figure 3).

Figure 3 MRI of pelvis with anal probe in situ, confirming correct placement for sEMG detection.

The results are analysed by the receiver to provide numerical values. The values are displayed as a target shaped diagram depicting locational functionality (figure 4 & 5), giving a clear representation of precise areas of weakness in the pelvic floor.

Figure 4 The results can be displayed in three views.

Figure 5 Sensors are grouped together according to the muscle they represent.

The results are displayed on a hand held device in both numerical and diagrammatic formats (figure 6).

Figure 6 Results are displayed on screen in greyscale on target or numerical value.

An independent study tested MAPLe on 229 asymptomatic healthy participants. The study confirmed accurate probe placement to ensure sEMG correlated with correct muscular group, and identified a normal range (27). MAPLe is currently used to provide biofeedback for patients with FI by identifying and targeting muscles with reduced sEMG via visual and electrical stimulation.

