The role of sEMG in clinical assessment of FI has been limited to research and has not been correlated with current gold standard techniques. This study aims to investigate the sEMG of symptomatic patients using MAPLe. The study will test the non-inferiority of MAPLe against HRAM and AUS in assessing FI. Non-inferiority of a test is defined as the test being no worse than the competitor. The study will aim to identify if particular patient groups have closer correlation

between symptom profiles and FI scores and sEMG results, and whether sEMG improves following treatment. The study will endeavor to identify the clinical utilisation of sEMG in FI.

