3.1 Assessment and Management of Risk

The table below summarise the risks and mitigations of all test above standard care that are being performed in a table:

Intervention	Potential risk	Risk Management
Assessment with MAPLe device	The device will be placed anally and record sEMG, not providing stimulation. As the device will be used in the same nature as current assessment devices no additional risk is perceived.	Performed by trained operator.

4. Objectives

Primary: To determine the role of MAPLe in the assessment of FI in defined patient groups.

Secondary: To determine if targeted treatment is achieved following assessment with MAPLe.

5. Trial design

This is cohort study of participants with symptoms of faecal incontinence. It will take place across two hospital trusts, both able to provide specialist pelvic floor services and facilities required to meet the needs of the study and follow up required by the participants. The use of two sites aims to increase the yield and diversity of participants. The sample size for the study is 120 participants.

Following a stringent selection and recruitment process, participants will be invited to a designated ARP session where they will be consented, complete an incontinence and quality of life questionnaire, and undergo ARP assessment. This will comprise of the current gold standard, AUS and HRAM, and additional assessment with MAPLe using a standardised protocol. Through undertaking all three tests participants will act at their own controls. Participant participation will conclude following ARP assessment unless treatment is deemed necessary by their local MDT. These participants will be followed up at 6 months with interval MAPLe assessment and incontinence and quality of life questionnaire.

The results will undergo statistical analysis to determine non-inferiority of MAPLe in assessing FI. For analysis participants will be allocated to the following groups: fistula/chronic perianal conditions, obstetric injury <12 months, obstetric injury >12months, neurogenic. Each group will be analysed using symptoms profile and MAPLe results to identify correlation. Comparison of MAPle results pre and post treatment will determine if targeted treatment has been achieved.

An expert panel of pelvic floor specialists will be formed to determine the additional benefit of MAPLe in a clinical context. The panel will consist of 3-6 specialists within the field. To reduce bias,

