8.4 Subsequent assessments and procedures

The ARP results for each participant will be discussed at their local multi disciplinary team meeting in accordance with current practice. Participants who are offered treatment will be followed up at 6 months in their recruiting trust for repeat assessment with MAPLe. Participants who are offered neuromodulation will receive interval assessment with MAPLe during the placement of the implanted device. Should not follow up be offered participation is complete.

A schedule of all trial assessments and procedures is set-out in Appendix 1.

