11.2 Secondary outcome(s)

The secondary outcome is to determine if following assessment with MAPLe targeted treatment is achieved. This will be defined by improvement in physiological assessment with MAPLe and incontinence questionnaires. This will be measured at 6 months following the end of recruitment at the end of study.

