11.5.2 Secondary outcome analysis

To determine if targeted treatment has been achieved participants will be grouped according to the treatment received: biofeedback, neuromodulation, rectal irrigation, and surgery.

Statistical comparison between MAPLe results pre and post treatment for each participant per group will be performed and analysed.

12. Record keeping and archiving

At the end of the trial, all essential documentation will be archived securely by the CI for a minimum of 20 years from the declaration of end of trial.

Essential documents are those which enable both the conduct of the trial and the quality of the data produced to be evaluated and show whether the site complied with all applicable regulatory requirements.

The sponsor will notify sites when trial documentation can be archived. All archived documents must continue to be available for inspection by appropriate authorities upon request.

13. Oversight Committees

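### The secondary outcome counts improvement after treatment as targeted treatment achieved following MAPLe, but the design measures only response to treatment

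*Combined protocol and SAP*

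**What the plan says.** The secondary objective in section 4 is "To determine if targeted treatment is achieved following assessment with MAPLe". Section 11.2 turns it into a criterion: "This will be defined by improvement in physiological assessment with MAPLe and incontinence questionnaires". The Summary states the inference for MAPLe alone: "Comparative analysis of participant pre and post treatment MAPLe results will identify if targeted treatment has been achieved". Section 5 repeats it in its paragraph on analysis. Section 11.5.2 gives the analysis: "To determine if targeted treatment has been achieved participants will be grouped according to the treatment received" (biofeedback, neuromodulation, rectal irrigation or surgery), with MAPLe compared before and after treatment within each group.

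On how treatment is chosen, section 8.4 says: "The ARP results for each participant will be discussed at their local multi disciplinary team meeting in accordance with current practice". Anyone offered treatment returns at 6 months.

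**The concern.** The objective is about what treatment was aimed at, or what directed it. The criterion is about whether the participant got better. These can come apart. A participant may improve on treatment chosen without regard to MAPLe, and a participant whose treatment followed the MAPLe finding exactly may not improve.

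If the plan is followed as written, improvement after usual treatment can be reported as successful targeting following MAPLe, on the study's only secondary outcome. The reverse error is also open. The background (section 3, Treatment) says that repeat physiology after treatment has shown no improvement. If that carries over to surface EMG, a null MAPLe change would be read as failed targeting when it says nothing about targeting.

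The same section shows the hazard. It reports good outcomes in 53% after percutaneous tibial nerve stimulation, then a randomised trial with no significant clinical benefit over sham.

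**Working it through.** **1. Could the outcome be met if MAPLe influenced no decision?** Take that as the hypothesis and look for anything in the plan that would contradict it.

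- Comparator: none for treatment outcome. Section 5 calls participants their own controls, but this refers to having all three tests.
- Grouping: by treatment received, not by whether MAPLe directed the treatment.
- Treatment decision: the local MDT under current practice, with no rule for using MAPLe.
- Record: section 10.4 lists demographic and history items and says that investigation results go on the CRF. No section specifies a treatment rationale, or the muscle or site treated because of MAPLe. The CRF itself is not in the documents.
- Expert panel: Question 1 in section 5 asks whether management changes once MAPLe is shown. It concerns panellists' views on supplied cases and feeds the primary outcome (11.1, 11.5.1), not the treatment given.

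Nothing contradicts the hypothesis, so the outcome can be met without any MAPLe influence.

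**2. The plan's own figure.** Section 11.3 sets 30 × 4 = 120, which reproduces as arithmetic. The four groups are causes of incontinence, not treatments, and no alpha, power or effect size is given. The figure sets no group size for this outcome.

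**3. Cited response rates.** Section 3 gives 70-80% of patients with a 50% symptom improvement after biofeedback (with later studies finding none), symptoms improved by 44% with irrigation, and 83% still improved at 3 years after sacral nerve stimulation. These are symptom figures. Section 11.2 joins MAPLe and questionnaires with *and*, and 11.5.2 analyses MAPLe only. The documents give no rate of MAPLe improvement, so the rate of meeting the joint outcome cannot be derived.

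**4. Regression to the mean, as an illustration.** Assume no treatment effect, standard normal measures, treatment for the worst fraction f on some selector, correlation c between selector and baseline MAPLe, and test-retest correlation r. Assume also that the retest relates to the selector only through baseline. Then

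expected change = c × (1 − r) × φ(z_f)/f,

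where φ(z_f)/f = 0.798 for f = 0.5 and 0.424 for f = 0.75. For f = 0.5, c = 1 and r = 0.6 this is 0.4 × 0.798 = 0.319 SD. The last column is the simulated chance (40,000 studies per setting) that a two-sided 5% paired t-test is significant in the improved direction, against a nominal 2.5%. Ranges run from r = 0.6 to r = 0.9.

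| f | c | n | Expected change (SD) | Significant improvement |
|---|---|---|---|---|
| 0.5 | 1.0 | 30 | 0.32 to 0.08 | 53% to 16% |
| 0.5 | 1.0 | 15 | 0.32 to 0.08 | 28% to 10% |
| 0.75 | 1.0 | 30 | 0.17 to 0.04 | 18% to 7% |
| 0.5 | 0.5 | 30 | 0.16 to 0.04 | 16% to 7% |
| 0.5 | 0.3 | 30 | 0.10 to 0.02 | 8% to 4.5% |

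The n = 15 row is there because half of 120 is 60 treated, and 60/4 = 15 per treatment group on average. A group of 30 needs unequal groups or more people treated. Setting c = 1 means a strict cut-off on the measure that is later repeated, and the protocol has no such rule.

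**The case against.** The best defence is that this is a first cohort study of the question, that *following* is a word about time, and that the Rationale asks only "whether sEMG improves following treatment". A before-and-after comparison answers that. This stands: the comparison is worth making, and no control arm is needed to report change after treatment. It does not rescue the step from change to targeting, which the Summary and sections 5, 11.2 and 11.5.2 all take.

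It is also fair to say that 11.2 does give an operational definition, so the outcome is not undefined. The trouble is what the definition measures. The Rationale describes MAPLe biofeedback as "identifying and targeting muscles with reduced sEMG via visual and electrical stimulation", and if targeting means that, MAPLe change is relevant. Even then the protocol specifies no record of which muscle or site was treated because of MAPLe.

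Three stronger readings are tempting, and the documents support none of them.

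- A reader might take 70-80% as the rate at which usual care would meet the outcome. Those are symptom responders, and the outcome also requires MAPLe improvement.
- A reader might take 53% as the false-positive rate. It needs full truncation on the re-tested measure, r = 0.6 and 30 per treatment group.
- A reader might conclude that the MDT does not see MAPLe. The Summary has participants "undergo routine ARP with high resolution manometry (HRAM) and anal ultrasound (AUS), and additional assessment with MAPLe", which separates the two. But sections 5 and 8.3 place MAPLe in the physiology session, and 10.2 puts all data in the local notes. The point is left open, and the attribution problem holds either way.

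**Conclusion.** The concern holds as a fault in how the outcome is defined. Section 11.2 sets a rule that measures response to treatment and labels the result targeting following MAPLe. Following the plan exactly could credit MAPLe with usual-treatment effect, time or regression to the mean, and a null result would be equally uninformative. This conclusion rests on the text alone.

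The size is illustrative. In 30 participants, with the worst half treated and r between 0.6 and 0.9, regression to the mean alone gives significant improvement in about 4.5% to 16% of studies for a selector correlating 0.3 to 0.5 with baseline MAPLe. Under full truncation the upper limit is 53% at n = 30 and 28% at n = 15. The selection fraction, both correlations, the group sizes and the test are assumptions.

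The primary outcome and participant safety are not affected. The qualification on records also stays: the CRF is not available, so it can be said only that the protocol specifies no link.

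**What to change.** In the Summary, section 4, section 5, section 11.2 and section 11.5.2, restate the secondary objective, outcome and analysis as change in MAPLe and in incontinence scores from before treatment to the 6-month follow-up, by treatment received. State that no inference about MAPLe targeting is drawn. Section 11.5.2 should name the incontinence scores, since it now covers MAPLe only. Section 5 already plans the questionnaires at 6 months.

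This needs no extra participants, visits or tests. It does need a protocol amendment, approved before use (section 14). The real cost is that the study gives up the targeting claim, which its design cannot support.

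Optional: if the sponsor wants to keep a targeting claim, the MDT record should capture whether the MAPLe finding directed the treatment or the site treated. That adds an item at each MDT discussion and requires settling whether the MDT sees MAPLe. The main fix does not depend on it.

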11.3 Sample size calculation

The sample size has not been formally calculated at this time. This is due to no previous studies on this area being performed. A pilot study to identify the 'normal' measurements for the MAPLe stipulated 30 participants per group to identify a statistically significant result. Accounting for 4 participant groups a sample size of 120 has been set.

11.4 Planned recruitment rate

Participants will be recruited throughout the duration of the study. An anticipated recruitment rate is 2-3 participants per week over 12 months to meet the sample size.

11.5 Statistical analysis

11.5.1 Primary outcome analysis

Non-inferiority testing of MAPLe will be performed using Bland-Altman method. Correlation between MAPLe and AUS for location of sphincter abnormality will be identified. Correlation between MAPLe and HRAM for functional abnormalities will be identified.

Participants will be allocated a patient group dependent on the cause of FI:

- □ Fistula/ chronic perianal conditions
- \Box Obstetric injury <12 months
- \Box Obstetric injury > 12 months
- □ Neuropathic

Each group will be analysed using correlation studies and regression analysis to determine which groups benefit from MAPLe assessment.

The clinical benefit of the addition of MAPLe assessment will be determined from the analysis of the results of the expert panel.

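### The planned Bland-Altman test cannot show whether MAPLe is non-inferior to HRAM or AUS: it does not fit the measurements, and no margin or acceptable limits are stated

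*Combined protocol and SAP*

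**What the plan says.** The Summary (section 2, statistical methodology) states "Non-inferiority testing of MAPLe in the assessment of FI will be performed using Bland Altman method" and adds "MAPLe will be tested against HRAM and AUS". Section 11.5.1 repeats the method: "Non-inferiority testing of MAPLe will be performed using Bland-Altman method". The Rationale in section 3 gives the same aim, "The study will test the non-inferiority of MAPLe against HRAM and AUS in assessing FI", and explains the term: "Non-inferiority of a test is defined as the test being no worse than the competitor". Section 5 says "The results will undergo statistical analysis to determine non-inferiority of MAPLe in assessing FI" and describes the routine assessment as follows: "This will comprise of the current gold standard, AUS and HRAM".

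The measurement scales are given elsewhere in section 3. For MAPLe, "Each sensor detects the sEMG activity in mV for the most proximal muscle fibers". HRAM pressures are in mmHg. AUS is an image of the internal and external sphincters. Sections 3 and 7 say that MAPLe also shows where activity is reduced or increased.

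After naming Bland-Altman, section 11.5.1 plans to correlate MAPLe with AUS for the location of sphincter abnormality and with HRAM for functional abnormality. It then plans correlation and regression within four patient groups, and an expert-panel analysis.

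**The concern.** Bland-Altman analysis takes the difference between two readings of the same quantity in the same unit. It then asks whether the limits of agreement are narrow enough by a standard set beforehand. The plan meets neither condition. The devices do not report one quantity in one unit, and nothing says how close is close enough or how much worse is too much.

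At stake is the first analysis named for the primary outcome, and an aim repeated in the Summary, Rationale and Trial design. A statement that MAPLe is, or is not, non-inferior would have no basis in the stated method. If cut-offs or a margin were chosen after the results were seen, the conclusion would not be credible.

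**Working it through.** **1. The plan's own figure.** Section 11.3 gives 30 per group and 4 groups: 30 × 4 = 120, which reproduces. The section says that no formal calculation was done. It states no alpha, power, SD or margin, so 120 is not tied to any non-inferiority test.

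**2. The scales side by side.**

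| Comparison | MAPLe | Comparator | Can a difference be formed? |
|---|---|---|---|
| MAPLe vs HRAM | sEMG, mV | pressure, mmHg | No: different quantities and units |
| MAPLe vs AUS | location of reduced or increased activity | location of sphincter abnormality | No numerical difference: shared attribute, but categorical |

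**3. Would standardising rescue the HRAM comparison?** The plan does not propose it. If both readings were converted to within-sample z-scores, the mean difference would be 0 by construction. The limits would be ±1.96 × √(2(1 − r)), where r is the correlation:
- r = 0: ±2.77 SD
- r = 0.5: ±1.96 SD
- r = 0.9: ±0.88 SD

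The limits only restate r, and an acceptable width would still be needed.

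No raw-unit example is worked here. The only HRAM values in the documents are resting pressures, and the MAPLe protocol in Appendix 5 goes from stabilisation straight to squeeze, with no resting recording step.

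**4. Is there a criterion?** None appears in sections 2, 3, 5, 11.3 or 11.5. The definition in the Rationale could be read as a margin of zero, but it does not say on what measure MAPLe must be no worse.

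**5. What agreement and association could show.** All prevalence, kappa, correlation and discordance values below are assumptions.
- *Kappa, one rating per participant.* Assumed true kappa (κ) 0.4 to 0.8, equal marginals, half-width = 1.96 × SD from 40,000 simulated tables per setting. With 30-70% abnormal it is 0.11-0.18 at n=120 and 0.22-0.36 at n=30. As a check at 50% abnormal and n=120, 1.96 × √((1 − κ²)/n) gives 0.107 for κ = 0.8 and 0.164 for κ = 0.4.
- *Higher prevalence.* All participants are symptomatic. At 90% abnormal (12 normal of 120, 3 of 30) the kappa half-width is 0.20-0.27 at n=120 and 0.50-0.58 at n=30. For negative agreement it is 0.18-0.26 and 0.49-0.56.
- *Correlation.* Fisher z, ±1.96/√(n − 3). For r from 0 to 0.7 the half-width is 0.18 falling to 0.09 at n=120, and 0.36 falling to 0.20 at n=30.

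**6. What n=120 could show if non-inferiority were kept.** Take a paired proportion with true difference 0, one-sided 2.5% and 10-40% of pairs discordant. The half-width is 1.96 × √(discordant/n):
- 1.96 × √(0.10/120) = 0.06
- 1.96 × √(0.40/120) = 0.11

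Power is Φ(margin/√(discordant/n) − 1.96). For an illustrative margin of 10 points it falls from 93% to 41%. For 15 points it falls from above 99% to 74%. These margins are not proposals.

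**The case against.** The strongest reply is that non-inferiority is not what the study rests on. The section 4 objectives and the primary outcome in 11.1 do not mention it. The two sentences that follow the Bland-Altman statement already set out workable comparisons with AUS and HRAM. No treatment allocation, safety rule or sample size depends on this test. All of that stands, and it limits the point to one strand. It does not rescue that strand, because correlation, regression and panel opinion do not show non-inferiority without a criterion.

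It can also be said that MAPLe and AUS do share something. That is right. A reader might infer that MAPLe has nothing in common with either comparator, but sections 3, 7 and 11.5.1 show that location is common to MAPLe and AUS. A categorical comparison is therefore feasible. It is not a Bland-Altman analysis, and it too lacks a criterion.

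Finally, normal/abnormal status or standardised scores might be what the authors had in mind. The plan states neither, and each would still need a margin or acceptable limits.

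**Conclusion.** The point holds for the non-inferiority strand. As specified, it cannot be carried out meaningfully against HRAM, does not apply to AUS, and has no rule by which any result would pass or fail. This is an error in the stated method and not only missing detail, because following the plan literally would give an unsupported conclusion in either direction. It rests on the documents' own descriptions of the three tests; the precision and power figures rest on the assumptions stated with them.

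Two stronger readings are not supported. A reader might infer that the whole primary analysis fails, but the outcome in 11.1 is defined by identification of abnormalities, correlation with symptoms and the expert panel, and these can still be addressed. A reader might also infer that MAPLe is inferior or that 120 is too few. Without an endpoint and a margin, the documents allow neither conclusion.

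**What to change.** Choose one route and write it into the plan before data are analysed.

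**A. Agreement and association.** Remove the Bland-Altman non-inferiority test from the Summary and 11.5.1, and replace the non-inferiority wording in the Rationale and section 5. Report with 95% confidence intervals:
- *MAPLe vs AUS:* kappa plus positive and negative agreement, for abnormal/normal status and for location, with intervals clustered by participant where several locations are rated. State in advance which AUS abnormalities count. AUS reads structure, including the involuntary internal sphincter, whereas section 3 describes EMG as a test of voluntary muscle. Low agreement would not by itself show that MAPLe is worse.
- *MAPLe vs HRAM:* normal/abnormal agreement, plus correlation on the manoeuvres common to the HRAM and MAPLe protocols in the appendices (squeeze, endurance squeeze, push, cough).
- Fix the cut-offs and location categories in the plan. Section 3 mentions a MAPLe normal range without values and gives only a resting range for HRAM.

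**B. Keep non-inferiority.** Name one endpoint on a common scale, justify a margin and state what n=120 can show. Expert-panel Question 2 (HRAM with AUS against MAPLe with AUS) is a candidate, but it has no stated reference diagnosis, number of cases or margin.

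**Cost.** Neither route needs extra tests on patients. Route A gives up the non-inferiority claim. An amendment is likely to be needed because a stated aim changes, a CRF field for status and location may be needed, and cut-offs must be sourced. Precision is limited as shown, and no figure is given for clustered location ratings. The n=30 figures assume equal groups, for which no quota is stated, so per-group results should be labelled descriptive.
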